המרכז הרפואי תל-אביב
ע"ש סוראסקי
רפואה מובילה ואנושית

Proposed Study Title

Study Title

Performance Evaluation Protocol for Sight Diagnostics' OLO CBC Analyzer by Ichilov oncology daily care center.

Contact Information

Name

[name]

Job Title

VP R&D

Institution

Sight Diagnostics

Address 1

[name]

Address 2

City, State, Zip

Tel Aviv

Country

Israel

Phone/Fax

E-mail	[contact]
--------	--------------------

Study Information

Tumor Type	N/A				
Areas of Interest	N/A				
# of Patients	50	Study Duration (Months)	1	Number of Sites	1
Site Names	Sight Diagnostics				

Hypothesis / Overall Objectives

Background:

The Sight OLO is a quantitative multi-parameter automated hematology analyzer intended for in vitro diagnostic use in screening capillary or venous whole blood samples collected in K₂EDTA blood collection tubes, or fingertip samples collected using the Sight OLO test kit microcapillary tubes. When used with the Sight OLO cartridge, the Sight OLO enumerates the following CBC parameters in whole blood: WBC, RBC, HGB, HCT, MCV, MCH, MCHC, RDW, PLT, NEUT%/#, LYMPH %/#, MONO %/#, EOS%/#, and BASO%/#.

The Sight OLO is indicated for use in point of care and clinical laboratories to identify and classify one or more of the formed elements of blood in children 3 months and above, adolescents and adults. In case a different intended use is required by the evaluating site, Sight should be informed in advance.

As there are great benefits in performing CBC tests from fingertip in oncologic patients, this study aims to establish OLO’s performance accuracy of CBC results for finger prick samples across the OLO reportable range, and particularly around relevant medical decision points. Additionally, the study will evaluate OLO’s compatibility to Ichilov oncology daily care center, while focusing on its effect of workflow and turnaround time.

Hypothesis:

The results of this study are expected to show good performance of OLO and its equivalence to the site's standard hematology system - Beckman Coulter DxH800 analyzer - in samples spanned over a wide clinical measuring range and covering medical decision points for WBC, HGB, PLT, and NEUT#. The medical decisions taken for treating chemotherapy patients at the oncology center are expected to remain equal when based on the results given by Sight OLO.

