OLO is hypothesized to allow shorter time to CBC results, by minimizing the time period from phlebotomy to results, currently prolonged due to the need to send blood samples from the oncology

daily care center to the central lab. By that, Sight OLO would improve workflow efficiency and provide care to patients in a reliable and accelerated fashion.

Study Description

Provide a concise overview stating the type of study, phase, design, and compounds

Study design:

This evaluation will include two studies:

1. A matrix study will compare a capillary sample collected via finger prick with a venous sample collected into a blood tube, both scanned on OLO.
2. A method comparison study will compare Sight OLO to Beckman Coulter DxH800 using a venous sample collected into a blood tube.

During a period of 2 weeks, approximately 50 whole blood samples will be collected from patients at the oncology daily care center.

Patient Enrollment:

- Each patient participating in the study will firstly fill and sign an Informed Consent Form (ICF). Subjects participating in the study will be rewarded with a coupon for coffee and cake.
- For de-identification purposes, study barcode stickers will be used for all of OLO scans, instead of the original patient identification details. An unblinded form will be used to match the de-identification barcode with the patient identification details (this form will remain at the center and will not be shared externally).
- Patient enrollment will be documented in a designated worksheet, using the study barcode stickers.
- The patient will be asked to rest for at least 15 minutes.

Phlebotomy and Scanning Flow:

During the routine blood collection, an additional venous sample will be collected in K₃EDTA tube as part of the study. The phlebotomy time will be recorded in the worksheet.

The first tube will get a study barcode sticker and remain in the daily care center at a room temperature of 18°C-26°C. The second tube will be sent to the lab to be scanned on Beckman Coulter DxH800, as part of the routine procedure.

Two consecutive finger prick samples will be collected from the 3rd and 4th fingers of the patient's non-dominant hand (in this order) and scanned on OLO, and the time of the first result will be recorded in the study worksheet.

Following two successful finger prick scans, the venous sample (collected previously for the study) will be scanned on OLO.

The following time points will be recorded in the study worksheet:

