Once all the predefined range groups are covered, the study will be completed and the results will be analyzed.

Statistical considerations:

Passing Bablok regression analyses will be performed for each measurand between:

- (1) The mean value given by OLO for the finger prick samples and the value given by OLO for the venous sample.

- (2) The value given by OLO for the venous sample and the value given by Beckman Coulter DxH800 for the venous sample.

Measurands invalidated by either OLO or Beckman Coulter DxH800 will be removed from all analyses.

The time to result will be compared between the time of first available finger prick results (from the scan on OLO) and the time of available venous results (from the routine scan on Beckman Coulter).

After study completion, medical records of the enrolled patients will be reviewed to evaluate whether the same clinical decision would have been taken when based on OLO results.

Environmental requirements:

- OLO should be placed on a stable bench (shared with no vibrating equipment) with enough space for the device and an adjacent surface for sample preparation. OLO's physical measurements are: 25.7X32.6X28.7 cm, 10 kg.
- Power supply - OLO is provided with a power supply unit which needs to be connected to a standard grounded power socket.
- Internet connectivity - not mandatory for operation but preferable for remote support and monitoring. LAN connectivity is preferable. Sight can provide 3G/4G dongle for cellular connectivity. It would be best to contact an IT person directly to understand whether there are special compliance requirements when connecting OLO to the local network/internet.
- Each blood tube should be kept at room temperature of 18°C-26°C throughout the day until the last scan is completed. The OLO operating temperature range is 18°C-30°C, relative humidity range is 20%-80%.
- The reference device must be calibrated and approved for use according to the lab standard operating procedures during the entire performance evaluation study. If any calibration process is performed during the study, Sight should be informed, preferably in advance, to be able to take the steps required to avoid interference with the method comparison (such as the removal of the samples scanned before/after the calibration).
- Results from the OLO can be exported as a CSV file through a USB drive and sent via email.

Sharing of results:

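### Passing-Bablok is the only stated accuracy analysis for all 19 measurands, although range is secured for only four; for narrow-range measurands its slope can mislead, so a paired-difference result should be added

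*Protocol*

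**What the plan says.** The Protocol, Statistical considerations, states the method and its scope: "Passing Bablok regression analyses will be performed for each measurand between" two pairs of values. Comparison 1 is "The mean value given by OLO for the finger prick samples and the value given by OLO for the venous sample". Comparison 2 is "The value given by OLO for the venous sample and the value given by Beckman Coulter DxH800 for the venous sample". No other accuracy statistic is named, and no condition on range or error is attached.

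The measurands are listed in the Background under Hypothesis / Overall Objectives: "WBC, RBC, HGB, HCT, MCV, MCH, MCHC, RDW, PLT, NEUT%/#, LYMPH %/#, MONO %/#, EOS%/#, and BASO", with the five differentials given both as percentage and as count.

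The finger-prick side is duplicated: "Two consecutive finger prick samples will be collected from the 3rd and 4th fingers". The venous sample gives one OLO value and one DxH800 value. The size is "approximately 50 whole blood samples will be collected from patients at the oncology daily care center".

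Table 1, under Study Population, sets range quotas for PLT, HGB, WBC and NEUT# only. These are the same four that the hypothesis names: "covering medical decision points for WBC, HGB, PLT, and NEUT"#.

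**The concern.** With a true slope of 1, Passing-Bablok centres on 1 when the two sides have the same error SD, or when the spread of true values is large enough to swamp the difference. Neither is secured for most of the panel. Comparison 1 sets a mean of two scans against a single scan, and comparison 2 sets two different analyzers against each other, so equal error cannot be taken for granted. Outside the four quota measurands, the spread of values is whatever the sample happens to give. MCHC, MCH and RDW are the likely narrow ones.

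There is a second, separate mechanism. If two patients share the same value on one side and differ on the other, their pairwise slope is zero or infinite. A count close to zero and reported in coarse steps, such as BASO#, can have so many of these pairs that the confidence limit has no upper bound.

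At stake is how the secondary part of the panel is read. A proportional bias produced by the method would look like a device fault, and an unbounded interval says nothing about accuracy. The Background puts the whole OLO reportable range within the study aim, so these measurands are not incidental.

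**Working it through.** **No figure to reproduce.** The protocol states no analytical SD, error ratio, reporting step or sample-size derivation.

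**Inputs from the protocol.** Measurands: 9 single (WBC to PLT) + 5 differentials × 2 = 19. With quotas: 4. Without: 19 − 4 = 15. Samples: about 50. Comparison 1: two scans averaged against one.

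**Assumed inputs.** True slope 1, intercept 0, normally distributed true values. Error SDs e_x and e_y are expressed as fractions of the between-patient SD. The standard Passing-Bablok estimate and its rank-based 95% CI were simulated for n = 50.

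**Error on each side of comparison 1.** Let s be the venous error SD and r the ratio of finger-prick to venous SD per scan. With venous on x, e_x = s and e_y = r·s/√2. The two are equal when r = √2 ≈ 1.41.

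**Hand check.** The ratio of total SDs, √[(1 + e_y²)/(1 + e_x²)], is not the Passing-Bablok estimate. It shows the direction and rough size of the shift.

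| Case | e_x, e_y | Hand check | Simulated median slope | CI excludes 1 |
|---|---|---|---|---|
| Equal errors | 0.5, 0.5 | 1 | 1.00 | 5% |
| Comparison 1, r = 1, small error | 0.3, 0.3/√2 | √(1.045/1.09) = 0.98 | 0.98 | 6% |
| Comparison 1, r = 1 | 0.6, 0.6/√2 | √(1.18/1.36) = 0.93 | 0.92 | 11% |
| Same, axes swapped | 0.6/√2, 0.6 | √(1.36/1.18) = 1.07 | 1.08 to 1.09 | 11 to 12% |
| Comparison 1, r = √2 | 0.5, 0.5 | 1 | 1.00 | 4% |
| Comparison 1, r = 2 | 0.5, 0.5 × 2/√2 | √(1.5/1.25) = 1.10 | 1.11 | 14% |
| Comparison 2, 2:1 imbalance | 0.4, 0.8 | √(1.64/1.16) = 1.19 | 1.23 | 38% |

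Size and direction both follow the assumed ratio. Averaging alone (r = 1) gives 0.84 and 21% when the venous error equals the spread (s = 1.0). At that same s, r = 3 gives 2.19 and 93%. These are extremes, not expectations.

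**Wide range.** A PLT-like measurand with 5% CV gave median slopes of 1.00 to 1.01 for r from 1 to 3. The CI excluded 1 in 8 to 10% of runs, including 9% at r = √2 where the errors balance. That excess therefore does not come from imbalance.

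**Ties.** BASO# was simulated with mean 0.02 to 0.03 and error SD 0.01 to 0.02.
- Step 0.01: slope and upper limit finite in every run.
- Step 0.1 on both sides: upper limit infinite in 36 to 81% of runs.
- Step 0.1 for the single scan, with the two-scan mean moving in steps of 0.05: infinite in 97 to 100%.
- EOS# (mean 0.15): slope finite at both steps, median 0.98 to 1.00; upper limit infinite in at most 0.1%.

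**The case against.** The strongest reply is that every magnitude above is assumed, and that range checks, difference plots and fallback methods normally belong in a statistical analysis plan, which is not at hand. The protocol sets no acceptance rule on the slope, so an interval that excludes 1 fails no stated test. It does not forbid a difference analysis, and it describes the work as an early comparison. The hypothesis rests on the four measurands that have quotas.

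Most of this stands, and it limits the point. It does not remove it. The protocol does not leave the method open: it fixes one regression for each measurand and names nothing else. A later plan could add checks, but it could replace the slope as the accuracy result for some measurands only by departing from that sentence.

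Three stronger readings are tempting and are not supported.
- *Averaging two scans makes comparison 1 biased.* It does so only if single scans are about equally precise. If finger-prick scans are about 1.4 times as variable as venous ones, averaging restores the balance. The documents give no ratio, so even the direction is unknown.
- *Unequal error causes the unbounded slope, for EOS as well as BASO.* The unbounded limit comes from ties. It appeared for BASO# at an assumed step of 0.1 and not at 0.01, and EOS# did not break down.
- *Passing-Bablok should be dropped for a fixed list including MCV and MONO.* Nothing was shown for those measurands, and RBC, HCT and LYMPH also lack quotas. A fixed list would be a preference; a rule based on observed spread and ties is better founded.

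**Conclusion.** The point holds as a conditional one and is worth acting on. For measurands without range quotas whose spread may be small against error, the stated analysis can show proportional bias where there is none. With 50 samples and errors assumed at 0.3 to 0.8 of the between-patient SD, the slope lies between about 0.92 and 1.23, and the 95% CI excludes 1 in about 6 to 38% of studies, against 5% with equal errors. The upper end needs a 2:1 error imbalance, for which the documents offer no evidence either way. Averaging alone gives about 6 to 12%.

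The infinite upper limit for BASO# is a separate problem and depends on a coarse reporting step that the protocol does not state.

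A reader might infer that the study's main accuracy conclusions are unsafe. They are not threatened by this point: WBC, HGB, PLT and NEUT# have planned range coverage, and the wide-range case run (PLT-like) showed a slope shift of at most 0.01.

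**What to change.** In Statistical considerations, keep Passing-Bablok for each measurand and add the following.

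1. For both comparisons and every measurand, report the paired mean or median difference with 95% CI and limits of agreement. The mean difference does not depend on the ratio of the two errors.
2. Make that the accuracy result for any measurand without a Table 1 quota whose observed spread is small against the error, or whose values are heavily tied. Fix the cut-off before the data are seen.
3. Estimate the finger-prick error from the duplicates: for within-patient differences d over n patients, single-scan SD = √(Σd²/2n), and the error of the two-scan mean is that divided by √2. This informs the capillary side only. The design repeats neither venous measurement, so venous error must come from elsewhere or be stated as unknown.
4. State that the limits of agreement in comparison 1 refer to a two-scan mean. With equal per-scan error and no other source of disagreement, they are √(1.5/2) = 0.87 times as wide as those for a single finger prick.

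This costs a few sentences and one extra table, with no new samples. The downside is that no proportional-bias claim is made for the measurands that fall under item 2, because a difference alone cannot show proportional bias.

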- Phlebotomy time
- Scanning time on the reference device at the lab.

This study design is illustrated in the study scheme below.

Study Requirements:

- All four scans will be performed within no more than 2 hours.
- All scans should be performed within 8 hours from phlebotomy.
- Venous samples should be collected in K₃EDTA tubes with a minimum volume of 700µL and kept at room temperature of 18°C-26°C throughout the day until the last scan is completed.
- The finger prick samples will be collected using lancets provided by Sight.
- If a finger prick scan is rejected, another sample will be collected from another finger, in the following order: non-dominant 3rd -> non-dominant 4th -> dominant 3rd -> dominant 4th. Up to 4 finger prick attempts will be performed **in total** for the two finger prick scans. If less than 2 finger prick scans are completed successfully, the sample should be excluded from the study. For each successful scan, the corresponding finger will be recorded in the worksheets.
- In case any of the venous scans are rejected, an additional repeat should be performed. Up to 3 attempts will be performed for each sample, and in case a 3rd failure occurs, the sample should be excluded from the study.
- Only 1 reference device should be used throughout this study - Beckman Coulter DxH800.
- A single operator will participate in the study.
- All relevant documents, including forms, worksheet and barcode stickers will be provided by Sight.

Primary endpoint:

Following the initial period of 2 weeks in which the samples will be randomly selected, the results will be evaluated to assess the coverage of the predefined range groups (specified in the study population section), in order to understand the timeframe and the type and quantity of samples required for completion of the study. If needed, a purposeful method for samples collection will be used, according to the missing ranges.

Purposeful Sampling Method - Study Design: A sample will be enrolled according to the result received from the routine CBC test from the same day (on Beckman Coulter DxH800) and incomplete range groups (specified in table 1). Once enrolled in the study, the samples collection and scanning will be performed in the same order as in the initial phase (illustrated in the study scheme below). During the purposeful method, the time to results will not be included in the analysis.

Secondary endpoint:

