- Given this is an early comparison study, results will be shared openly across both parties.
- CSV files with the results of OLO and de-identified PDF files with the results of the reference device should be shared regularly by the study coordinator.
- Study worksheets and enrollment forms will be delivered once completely filled.

Study Population

Brief description, setting and key inclusion/exclusion criteria

Inclusion Criteria:

Blood samples will be collected from oncologic patients older than 18 years old arriving at the oncologic daily care center of Ichilov hospital.

The sampling method will initially be randomized, though will aim to include both normal and abnormal ranges of blood counts (according to Beckman Coulter DxH800 as the reference analyzer), while covering wide analytical ranges with balanced distributions, focusing on values around medical decision points. Approximately 30 abnormal samples will be collected, with the ranges to cover specified in table 1 below. Note that a single sample can cover multiple ranges for different parameters. Additionally, approximately 20 normal samples will be collected, while for the purpose of this protocol, normal is defined as samples with values above the ranges specified in table 1 for all parameters (PLT>100X10³/μL, HGB>12.0g/dL, WBC>4.0X10³/μL, NEUT#>2.0X10³/μL), and with no flags on the site reference analyzer.

Table 1 - abnormal ranges

[figure not shown]
	Range	# of paired samples
PLT	<100X10 ³ /μL and >50X10 ³ /μL	2
	<50X10 ³ /μL and >30X10 ³ /μL	4
	<30X10 ³ /μL and >18X10 ³ /μL	4
	<18X10 ³ /μL	4
HGB	<12.0g/dL and >10.0g/dL	4
	<10.0g/dL and >4.0g/dL	4
WBC	<4.0X10 ³ /μL and >2.0X10 ³ /μL	2
	<2.0X10 ³ /μL	7
NEUT#	<2.0X10 ³ /μL and >1.0X10 ³ /μL	3
	<1.0X10 ³ /μL and >0.5X10 ³ /μL	3
	<0.5X10 ³ /μL	2

Exclusion Criteria:

- Visibly hemolyzed specimens (sample plasma should be checked for hemolysis by technician while selection of specimen from tube racks).
- Visibly clotted specimens (Reasonable to assume that samples processed with clinical reported results are not clotted).
- A sample that is not successfully scanned on OLO within 3 attempts (e.g. rejected due to irregular cell morphology, or microscopically visible hemolysis).

Study Schema

Please insert a graphic study schema or visual representation of trial design

Protocol revision signatures: This study protocol has been reviewed by Sight's key personnel with their signature approval for its use.

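### The removal and exclusion rules reach further than each analysis needs: a DxH800 invalidation deletes valid OLO-only pairs, and incomplete OLO sets leave time-to-result in a way that can favour OLO.

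*Protocol*

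**What the plan says.** Two regressions are planned per measurand. The first is the matrix study, which sets a capillary sample against one "with a venous sample collected into a blood tube, both scanned on OLO"; Statistical considerations define its two variables as "The mean value given by OLO for the finger prick samples and the value given by OLO for the venous sample". The second sets OLO venous against DxH800 venous. One removal rule follows for both: "Measurands invalidated by either OLO or Beckman Coulter DxH800 will be removed from all analyses".

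Time-to-result compares the first available OLO finger-prick result with the routine DxH800 result. The time of that first OLO result is entered in the worksheet (Phlebotomy and Scanning Flow).

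Study Requirements allow up to four pricks to obtain two successful scans. "If less than 2 finger prick scans are completed successfully, the sample should be excluded from the study". For venous scans up to three attempts are allowed, and "in case a 3rd failure occurs, the sample should be excluded from the study". The Exclusion Criteria add: "A sample that is not successfully scanned on OLO within 3 attempts". If purposeful sampling is used to fill the Table 1 ranges, "During the purposeful method, the time to results will not be included in the analysis".

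**The concern.** A removal rule should follow from what an analysis uses. Two of the planned analyses lose data they could use.

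(a) The first regression needs valid OLO values only. As written, it also loses a pair when OLO measured both samples properly and only the DxH800 invalidated the measurand.

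(b) Time-to-result needs one valid finger-prick result. It loses patients for lack of a second prick result or of a venous scan, neither of which enters the comparison. The loss depends on OLO's own performance: patients for whom OLO struggles are the ones who leave. A shorter time to CBC results is one of the protocol's stated hypotheses, so selecting on OLO success can flatter that result. Purposeful sampling cannot make up the loss, because its times are kept out of this analysis.

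**Working it through.** **Part (a).** The data each analysis needs, set against the rule:

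| Analysis | Values used | Removed when only the DxH800 invalidates? | Needed? |
|---|---|---|---|
| Regression (1) | OLO finger prick, OLO venous | yes | no |
| Regression (2) | OLO venous, DxH800 venous | yes | yes |

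The protocol gives no DxH800 invalidation rate. If it were 2, 5 or 10% for a measurand (assumed), the expected needless loss from regression (1) would be 50 × 0.02 = 1, 50 × 0.05 = 2.5 or 50 × 0.10 = 5 pairs. The venous-failure rule adds to this: it covers any venous scan, so three failed DxH800 scans would remove a complete OLO pair.

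**Part (b).** Inputs from the protocol: about 50 samples (30 abnormal + 20 normal = 50, which agrees), at most four pricks, two successes required. Input not given: the rejection rate per prick, q. I assume q = 0.1, 0.2, 0.3.

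*Which patients leave under the prick rule (independent rejections).* After a first success at attempt k, the patient is dropped only if all 4 − k remaining attempts fail, with probability q^(4−k). At q = 0.2:

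- first success at attempt 1: 0.2³ = 0.8% dropped
- attempt 2: 0.2² = 4%
- attempt 3: 20%
- attempt 4: 100%, at any q, because no attempt is left for a second success
- no success: 100%

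*How many leave.* P(fewer than 2 successes in 4) = q⁴ + 4q³(1−q):

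- q = 0.1: 0.0001 + 0.0036 = 0.0037, × 50 = 0.19
- q = 0.2: 0.0016 + 0.0256 = 0.0272, × 50 = 1.36
- q = 0.3: 0.0081 + 0.0756 = 0.0837, × 50 = 4.19

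Of these, patients with no valid prick number 50q⁴ = 0.005, 0.08 and 0.41.

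*What it does to the analysis.* In kept patients the first valid attempt is 1, 2 or 3 with weights (1−q)(1−q³), q(1−q)(1−q²) and q²(1−q)². In dropped patients with exactly one success, that success is equally likely at attempts 1 to 4, so its mean is 2.5. Their probability is 4q³(1−q). Restoring them at q = 0.2 gives (0.9728 × 1.2105 + 0.0256 × 2.5) / 0.9984 = 1.244.

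*Clustered rejections.* If rejections run in patients, I use a beta-binomial with mean q and intraclass correlation 0.3. This is an illustration; the protocol gives no value.

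| | q = 0.1 | q = 0.2 | q = 0.3 |
|---|---|---|---|
| Independent: dropped of 50 | 0.19 | 1.36 | 4.19 |
| of whom no valid prick | 0.005 | 0.08 | 0.41 |
| Mean first valid attempt, kept | 1.106 | 1.211 | 1.305 |
| with one-success patients restored | 1.111 | 1.244 | 1.396 |
| shift | 0.005 | 0.03 | 0.09 |
| Correlation 0.3: dropped of 50 | 2.08 | 5.13 | 9.15 |
| of whom no valid prick | 0.58 | 1.63 | 3.31 |
| Mean first valid attempt, kept | 1.08 | 1.15 | 1.21 |
| with one-success patients restored | 1.12 | 1.25 | 1.37 |
| shift | 0.04 | 0.10 | 0.16 |

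Patients with no valid prick have no first attempt and cannot enter these means; only a separate count shows them. Drops through a third OLO venous failure are not in the table. They would add 50q³ = 0.05, 0.4 or 1.35 if the same rates applied to independent venous scans and no patient were already lost under the prick rule. All counts take the full 50 as initial phase, which is the upper case.

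**The case against.** On (a), one common sample set for both regressions can be defended. No regression compares finger prick with DxH800 directly; the link runs through OLO venous, and using the same samples keeps both steps on one set. The protocol does not give this reason, and the common set could be reported as a sensitivity analysis. A pair without a valid DxH800 value also cannot be placed in a Table 1 range for that measurand, since ranges are set "according to Beckman Coulter DxH800 as the reference analyzer". That stands, but the pair remains usable in the regression. A reader might infer that regression (1) is biased. Nothing in the protocol supports this.

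On (b), the removal sentence speaks of measurands and follows the regressions; the time-to-result loss rests on the study-level exclusions alone. How missing times are handled may be set out in an analysis plan that is not at hand. This limits the point but does not remove it, because exclusion from the study is stated outright.

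A reader might also infer that the rules remove only late or absent results. They do not. Under independence a quarter of the one-success patients had their result at the first attempt, and patients lost to a failed OLO venous scan already had two good pricks and are not shown to be late. Nor does every rejected prick remove a patient: one or two rejections with two successes stay in. The contrast of attempt 2.5 with 1.1 to 1.3 compares subgroups; the effect on the mean is the small shift shown above. Finally, attempts cannot be turned into minutes or set against laboratory turnaround from the protocol, so no threat to the time hypothesis of known size is shown.

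**Conclusion.** The point holds in a limited form and should be fixed, because the repair is cheap and has to be in place before data collection.

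(a) The rule discards valid OLO pairs from regression (1). The cost is precision, of unknown size.

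(b) The prick rule makes exclusion from time-to-result more likely the later the first result, and certain at attempt 4 or with no result. The selection can therefore favour OLO. Its size depends on rejection rates that the protocol does not give. With independent rejection at 10% it is negligible (0.2 of 50 dropped, shift 0.005 of an attempt); at 30% it reaches 4.2 of 50 and 0.09. The larger figures, 2.1 to 9.1 of 50 and a shift of 0.04 to 0.16, need the assumed correlation of 0.3. A conclusion that the time comparison is invalid, or that OLO's saving is materially overstated, would go beyond the document.

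**What to change.** - Apply invalidation per comparison: regression (1) drops a pair only when OLO invalidated the measurand, regression (2) when either device did.
- For time-to-result in the initial phase, keep every patient with at least one valid finger-prick result, whatever happens to the second prick or the OLO venous scan. Report beside it the number with no valid OLO finger-prick result.
- Log failed scan attempts as well as successful ones (the worksheet now asks for the finger of successful scans only), and report OLO rejections.
- Reconcile the three-attempt limit in the Exclusion Criteria with the four-prick allowance in Study Requirements. The Exclusion Criteria do not say which scans the limit covers.

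The cost is slightly more logging, analysis sets that differ between the two regressions, and possibly a less favourable time saving. No extra patients or samples are needed.

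### Read literally, the removal and exclusion rules limit the treatment-decision review to cases where OLO gave a result

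*Protocol*

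**What the plan says.** Four places in the Protocol bear on this.

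- **Hypothesis.** Treatment decisions for chemotherapy patients are "expected to remain equal when based on the results given by Sight OLO".
- **Statistical considerations.** After listing the two Passing-Bablok comparisons, the text says "Measurands invalidated by either OLO or Beckman Coulter DxH800 will be removed from all analyses". Under the same heading, after the time-to-result paragraph, comes the decision review: "After study completion, medical records of the enrolled patients will be reviewed to evaluate whether the same clinical decision would have been taken", on the basis of OLO results.
- **Study Requirements.** For finger pricks, with up to four attempts in total: "If less than 2 finger prick scans are completed successfully, the sample should be excluded from the study". For venous scans: "in case a 3rd failure occurs, the sample should be excluded from the study".
- **Exclusion Criteria.** One criterion is "A sample that is not successfully scanned on OLO within 3 attempts". The examples given are irregular cells and hemolysis seen only under the microscope.

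No section says how a patient or measurand without an OLO result counts in the decision review, or that such losses are to be counted and reported.

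**The concern.** A regression needs two numbers, so a value that OLO did not release has to drop out of it. The decision review asks a different question. If OLO gives no usable neutrophil or platelet count and the decision depends on it, no decision can be based on OLO for that patient. That is information about the hypothesis, not merely a missing value.

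A removal rule that covers all analyses, together with exclusion of samples OLO cannot scan, makes the comparison depend on the evaluated device having worked. The Protocol's own examples tie rejection to the state of the blood, so the losses need not be random. That they would be commoner in the abnormal samples the study seeks is plausible, but it is an inference; the Protocol gives no data on it. At stake is whether a finding of equal decisions describes the patients of the daily care center or only those for whom OLO returned a value.

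**Working it through.** **Inputs from the Protocol.** About 30 abnormal and about 20 normal samples, 30 + 20 = 50, which matches the stated total. Table 1 asks for 4 samples with PLT below 18 and 2 with NEUT# below 0.5 (both ×10³/μL). The Protocol states no agreement target, OLO failure rate or invalidation rate, so every failure count below is an assumption.

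**Effect on agreement.** Let N be the patients in the review, f those without a usable OLO result, and a those with the same decision. Agreement among patients with results is a/(N−f); over all patients it is a/N. The gap is [a/(N−f)] × (f/N), which is positive whenever f and a are above zero.

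With N = 50 and every evaluable decision the same (a = 50−f):

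| f (assumed) | Among patients with results | Over all patients | Exact 95% CI, all patients |
|---|---|---|---|
| 1 | 49/49 = 100% | 49/50 = 98% | 89.4–99.9% |
| 2 | 48/48 = 100% | 48/50 = 96% | 86.3–99.5% |
| 5 | 45/45 = 100% | 45/50 = 90% | 78.2–96.7% |
| 10 | 40/40 = 100% | 40/50 = 80% | 66.3–90.0% |

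With two differing decisions and f = 5, the figures are 43/45 = 95.6% and 43/50 = 86.0%.

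**Small range groups.** One failure beside the 4 valid samples with PLT below 18 gives 4/4 = 100% against 4/5 = 80%. One beside the 2 valid samples with NEUT# below 0.5 gives 2/2 = 100% against 2/3 = 67%. Collection continues until the range groups are filled, so failed samples may simply be replaced and leave no trace.

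**What the retry rules imply for whole samples.** Assume independent attempts, each rejected with probability p.

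- Fewer than two successes in four pricks (sample excluded): 4(1−p)p³ + p⁴ = 0.37%, 2.72%, 8.37% for p = 10%, 20%, 30%.
- No success in four pricks: p⁴ = 0.01%, 0.16%, 0.81%.
- Three venous failures: p³ = 0.1%, 0.8%, 2.7%.

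Most samples excluded on the finger-prick rule therefore have exactly one successful scan, and a sample lost to venous failure already has two successful finger-prick scans. Those patients do have an OLO result. Under independence, complete absence of a result is rare. If rejection comes from the patient's blood, as the exclusion criterion's examples suggest, retries help less and the share is higher.

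**Invalidated measurands.** Let q be the chance that one of the four decision measurands is invalid on all of a patient's OLO scans. The share of patients lacking at least one is q if the invalidations coincide completely, and 1−(1−q)⁴ if they are independent. For q = 2%, 5%, 10% this runs from 2%, 5%, 10% to 7.8%, 18.5%, 34.4%. These are ranges under assumption, not estimates.

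**The case against.** The strongest reply is textual. The removal sentence follows directly on the regressions and shares their vocabulary, so it could mean all the regression analyses. The exclusions are worded for samples, while the review covers enrolled patients, and enrolment precedes scanning. A reader might infer that patients with OLO failures are certain to leave the review and that agreement will be overstated. The Protocol does not go that far. It does leave the matter open, and its literal wording, all analyses and exclusion from the study, points towards removal.

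Second, the hypothesis is phrased in terms of results that OLO gives, so agreement among valid results is a legitimate conditional measure. That stands, and the measure should be kept. Alone, it does not show that decisions for the center's patients would be unchanged.

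Third, the Protocol defines no agreement statistic, and denominators are often left to an analysis plan. That stands too, and their absence is not the criticism. The criticism is of a removal rule the Protocol does fix and words without exception.

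Fourth, a reader might count each missing OLO result as a changed decision. The documents do not support this. A rejected scan shows no different decision, and merging the two confuses availability with concordance. It would also charge visibly hemolyzed or clotted specimens to OLO.

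Finally, the 0.37%, 2.72% and 8.37% above are tempting as the share of patients without an OLO result. They are not that share, because they include patients with one successful prick; with no successful prick the figures are 0.01%, 0.16% and 0.81%.

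**Conclusion.** The point holds in a limited form. Followed literally, the text confines the same-decision question to cases where OLO worked, and this can make the hypothesis of equal decisions look better supported than it is. The direction is arithmetic once all-patient agreement is taken as the measure: for any f above zero, and some concordant decisions, it is lower than agreement among patients with results. The size cannot be derived from the Protocol. The illustration of 98% to 80% against 100% rests on an assumed 1 to 10 of 50 patients without a usable OLO result and otherwise perfect agreement. The regressions are unaffected, since removal is unavoidable there.

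A related inconsistency needs settling: Study Requirements allow four finger-prick attempts in total, while the Exclusion Criteria drop a sample not scanned within three attempts without saying which scans are meant.

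**What to change.** - State that the removal of invalidated measurands applies to the Passing-Bablok regressions only.
- In the decision review, keep every enrolled patient with a valid DxH800 result, except those whose specimen is excluded as visibly hemolyzed or clotted.
- Class each patient as *same decision*, *different decision* or *no OLO-based decision possible*. The last means no successful OLO scan, or a needed WBC, HGB, PLT or NEUT# invalid on all of that patient's OLO scans.
- Report agreement twice: over all these patients, and among those with complete OLO results.
- Count DxH800 invalidations separately, since they are not OLO failures.
- Reconcile the four-attempt and three-attempt limits so that it is clear who is lost and why.

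The cost is Protocol wording. The patients have consented and the record review is already planned. The downside is a somewhat less favourable all-patient figure, shown beside the conditional one.
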